# 7.6.2.2 Secondary Efficacy Endpoints

Descriptive statistics for the secondary efficacy endpoints will be presented by treatment group and by study visit where appropriate.

Clinical status by the 11 category WHO Clinical Progression Scale, at Day 8 (±1).

The clinical status, as assessed on the 11-point WHO Clinical Progression Scale on Day 8 will be summarised by treatment group. The percentage of patients within each category will be presented and the 95% CI will be computed using the Goodman method for the multinomial proportions.

In case of missing clinical status on Day 8, the following approach will be used:

- If patient dies before or on Day 8  $\rightarrow$  clinical status = 10.
- Otherwise, the last observation carried forward (LOCF) approach will be used, where the last recorded clinical status for the same patient is carried forward to the missing clinical status on Day 8.

The clinical status on Day 8 between each dose of plitidepsin versus control arm will be compared using a proportional odds model. The model will be adjusted for the randomisation stratification factors. The odds ratios, 95% CIs, and 2-sided p-values for the comparison of each dose of plitidepsin versus control arm will be presented.

• Total duration of advanced oxygen support (high-flow nasal oxygen, ECMO, non-invasive ventilation or mechanical ventilation).

The total duration of advanced oxygen support (in days), defined as the number of days with any type of advanced oxygen support (eg, high-flow nasal oxygen, non-invasive mechanical ventilation, invasive mechanical ventilation or ECMO)

Duration of advanced oxygen support (days) = (date of last advanced oxygen support required – date of randomisation) + 1 – off-advanced oxygen support days

If last advanced oxygen support date is missing then date of death or the last visit or the last telephone contact with the patient, whichever occurs later, will be used.

The number and percentage of patients who required an advanced oxygen support together with total duration of advanced oxygen support (in days) will be summarised by treatment group. Only patients who required an advanced oxygen support will be included in the summary of the total duration of advanced oxygen support.

• *Percentage of patients in each study group requiring admission to ICU on Days 4, 8, 15, and 31.* 

The percentage of patients who require admission to ICU at some time from Day 1 to Day 4, from Day 1 to Day 8, from Day 1 to Day 15, and from Day 1 to Day 31 will be presented by treatment group. Clopper–Pearson 95% CI will be computed for the binomial proportions.

The difference in the percentage of patients who require admission to ICU at some time during each period between each dose of plitidepsin versus control arm will be presented for each dose of plitidepsin and the exact 95% CI will be computed for the difference in the percentage.

The percentage of patients who require admission to ICU at some time from Day 1 to Day 8 between each dose of plitidepsin versus control arm will be compared using a stratified logistic regression model. The model will be adjusted for the randomisation stratification factors. The odds ratios, 95% CIs, and 2-sided p-values for the comparison of each dose of plitidepsin versus control arm will be presented.

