## 2.2 Overall Study Design

This is a randomised, multicentre, open-label, controlled Phase 3 study in which adults requiring hospital admission and oxygen supplementation for management of moderate COVID-19 infection will be randomised in 1:1:1 to:

- Plitidepsin 1.5 mg arm: Patients will receive plitidepsin 1.5 mg/day intravenous (IV) in addition to dexamethasone on days 1 to 3;
- Plitidepsin 2.5 mg arm: Patients will receive plitidepsin 2.5 mg/day IV in addition to dexamethasone on days 1 to 3;
- Control arm: Patients will receive dexamethasone IV on Days 1 to 3. Additionally, in accordance with local treatment guidelines, patients in this group may receive a regulatory-approved antiviral treatment.

The study allows up to a total cumulative dose of 60 mg of dexamethasone base (calculation of the total dose will also include corticosteroids administered within 72 hours before the start of the study treatment and dexamethasone administered as premedication).

Randomisation will be stratified for 3 factors:

- Geographical region (Europe vs. Rest of the World);
- Charlson Comorbidity Index (0-1 vs. >1); and
- Barthel Index (≥90 versus <90)

From treatment initiation on Day 1, patients will be followed in the hospital for at least 4 days and then through Day 31 ( $\pm$ 3 days) or resolution/stabilisation of treatment-related adverse events (AEs), treatment-emergent adverse events (TEAEs) of special interest, and serious adverse events (SAEs). Patients discharged from the hospital prior to Day 8 will return to an out-patient clinic for assessments on Days 8 ( $\pm$ 1 day), and 31 ( $\pm$ 3 days). On Day 15 ( $\pm$ 1 day), patients will be followed up in remote or on-site visit (Appendix 4).

An independent Data Monitoring Committee (IDMC) will oversee study conduct (safety and primary endpoint), including analysis of summary safety data as per the trial requirements.

The study is expected to randomise approximately 609 patients (203 in each arm) over a period of 20 months.

Patients will be considered to be on study from the signature of the informed consent form until the end of the follow-up period, that is, completion of the protocol-specified follow-up visit on Day 31 ( $\pm$ 3 days) or until resolution/ stabilisation of treatment-related AEs, TEAEs of special interest, and SAEs that occurred through Day 31, whichever is longer.

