- 13 Clinical Status: Assessed using the 11-point WHO Clinical Progression Scale will be performed at screening, daily from Day 1 while hospitalised and on Days 8 (±1 day), 15 (±1 day), and 31 (±3 days), where 0= uninfected, no viral RNA detected; 1 = asymptomatic, viral RNA detected; 2 = symptomatic, independent; 3 = symptomatic, assistance needed; 4 = hospitalised, no oxygen therapy (if hospitalised for isolation only, record status as for ambulatory patient); 5 = hospitalised, oxygen by mask or nasal prongs; 6 = hospitalised, oxygen by NIV or high flow; 7 = intubation and mechanical ventilation, pO2/FIO2 ≥ 150 or SpO2/FIO2 ≥ 200; 8 = mechanical ventilation, pO2/FIO2 < 150 and vasopressors, dialysis or ECMO; 10 = dead.

- 14 Functional Status: Assessed by the Barthel index score (Appendix 3); the pre-baseline (ie, > 1 month prior to at screening) functional status should be recorded, in addition to Day 1 prior to initiating study treatment, at hospital discharge, and on Days 8 (±1 day), 15 (±1 day), and 31 (±3 days).

CONFIDENTIAL

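### A missing last date of advanced oxygen support is imputed to last contact with no cap at discharge, so a discharged survivor with an open episode can be counted on support for weeks at home unless the undefined off-support term removes those days

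*SAP*

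**What the plan says.** Total duration of advanced oxygen support is a secondary efficacy endpoint (SAP sections 3.3 and 7.6.2.2). Section 7.6.2.2 makes four statements about it.

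- The quantity is "defined as the number of days with any type of advanced oxygen support".
- It is computed as the date of last advanced support minus the "date of randomisation) + 1 – off-advanced oxygen support days". The off-support term is not defined.
- If the last date is missing, "then date of death or the last visit or the last telephone contact with the patient, whichever occurs later, will be used".
- "Only patients who required an advanced oxygen support will be included in the summary of the total duration of advanced oxygen support".

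The shell for Table 14.2.3.2 repeats the formula. It adds no cap and no footnote on imputed dates.

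Contact continues after discharge. Section 2.2 states: "Patients discharged from the hospital prior to Day 8 will return to an out-patient clinic for assessments on" Days 8 and 31. On Day 15 "patients will be followed up in remote or on-site visit". Appendix 4 puts the end-of-study visit at Day 31 (±3), and section 2.2 lets follow-up for adverse events run longer.

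The documents also collect data that limit when support can have ended. The WHO clinical status assessment "will be performed at screening, daily from Day 1 while hospitalised" (Appendix 4, footnote 13), and its category for non-invasive ventilation or high flow is an in-hospital state. Hospital status changes, including discharge, are dated in Listing 16.2.6.3. Oxygen status and its changes are dated in Listing 16.2.6.4.

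**The concern.** For a patient who dies in hospital while still on support, running the episode to death is sensible. For a discharged survivor, the latest of the three dates is normally the Day 31 visit, which says nothing about when support stopped. Applied literally, the rule produces a duration that the same database contradicts. The patient can have a recorded discharge, be a sustained-withdrawal event in the primary analysis and have a low WHO score on Day 15, yet be summarised as on high flow until about Day 31.

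The error always lengthens the duration. It also enters a summary restricted to users of advanced support, where the denominator may be small: section 8 records that recruitment stopped before 33% of events, and section 7.8 puts that point at 175 events over three arms. The addendum then splits the table into site ES40 and all other sites (Tables 14.2.3.2.1 and 14.2.3.2.2), so the cells become smaller still.

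**Working it through.** The plan states no numerical target for this endpoint, so there is no figure to reproduce. The check applies the plan's own formula to illustrative patients.

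**From the SAP.** Duration = (last date − randomisation date) + 1 − off-support days. A missing last date becomes the latest of death, last visit and last telephone contact. The last visit is on Day 31, with a window of Days 28 to 34.

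**Assumed.** Randomisation and start of support are on Day 1. No off-support days are subtracted. The patient survives and attends the last visit on Day 31.

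**One patient.** High flow on Days 1 to 5, discharge on Day 10, end date missing.

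- True duration: (5 − 1) + 1 = 5 days.
- Rule as written: (31 − 1) + 1 = 31 days, or 28 to 34 over the visit window.
- Capped at discharge: (10 − 1) + 1 = 10 days.
- Rule as written, with the 21 days after discharge counted as off-support: 31 − 21 = 10 days.

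**Other patients**, last visit on Day 31:

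| True last day | Discharge day | Rule as written | Days counted after discharge | Excess over truth |
|---|---|---|---|---|
| 4 | 8 | 31 | 23 | 27 |
| 5 | 10 | 31 | 21 | 26 |
| 7 | 12 | 31 | 19 | 24 |
| 10 | 15 | 31 | 16 | 21 |

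Starting support on Day 3 leaves both excess columns unchanged, because the two days before support come off the true and the imputed duration alike.

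**Arm mean.** The shift is the number of missing dates × 21 days ÷ number of users, taking discharge on Day 10 and counting only the days after discharge. User numbers are assumed.

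| Users in arm | One missing date | Two missing dates |
|---|---|---|
| 8 | 21/8 = 2.6 days | 42/8 = 5.3 days |
| 12 | 21/12 = 1.8 days | 42/12 = 3.5 days |
| 16 | 21/16 = 1.3 days | 42/16 = 2.6 days |

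Measured against the true end of support on Day 5, the excess is 26 days. With 20 users and a true mean of 5 days, one missing date gives (19 × 5 + 31)/20 = 6.3 days. With 40 users it gives (39 × 5 + 31)/40 = 5.65 days.

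**The case against.** The best defence has four parts.

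- **The trigger may be rare.** Table 14.2.3.2 draws on Listing 16.2.6.4, a dated log of oxygen status with no separate stop-date column. A later row on low flow or no oxygen would normally supply the end of support, and the rule would not be needed. The natural open episode is a patient still on support at the last record, for whom running to death or last contact is an ordinary convention. This stands as to frequency: the number affected is unknown and could be zero. It does not justify a rule that ignores discharge when a log is incomplete.
- **The off-support term may already cover it.** The formula starts at randomisation, so this term must already remove days before support began. Read with the definition of the endpoint, it could remove days at home too, which brings the 31-day example down to 10. This also stands as a possible reading. The SAP neither requires nor excludes it, so two programmers could report different results. Even the favourable reading leaves the days between the true end and discharge counted.
- **Nothing is tested.** No comparison of durations is planned, and the shell gives median and quartiles beside the mean. One or two extreme values hardly move a median. Accepted.
- **A loosely worded replacement could do harm.** Stopping at the first WHO score of 5 or less after support starts would cut off a later episode in a patient who steps down and then re-escalates. Section 7.6.1 itself acknowledges inconsistencies between the WHO scale and the recorded oxygen status. Both points are right, and the fix has to respect them.

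**Conclusion.** The rule should be changed, as a correction to a derivation and not as a threat to the trial's conclusions. As written it allows a discharged survivor with an open last episode to be counted on advanced support for about 16 to 23 days after leaving hospital (discharge on Days 15 to 8, last visit on Day 31), plus or minus 3 days for the visit window. This holds only if days after discharge are not taken out as off-support days. In an arm with 8 to 16 users, each such date moves the mean by 2.6 to 1.3 days. Those user counts, the Day 10 discharge and the number of missing dates are assumptions; the documents give none of them.

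A reader might infer two stronger things. One is that such patients will certainly be credited with support up to Day 31. The documents do not establish that, because the off-support term is undefined and a later row in the oxygen log would often close the episode. The other is that the rule decides which arm has the longer duration, or biases a treatment comparison. No comparison is planned for this endpoint, the same rule applies in every arm, and nothing indicates that missing dates differ between arms. What is affected is the reported mean, and possibly the quartiles, in a small denominator.

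**What to change.** In section 7.6.2.2, replace the sentence on the missing date with a rule that applies only to the last open episode and is counted from the last record showing advanced support. Set the end to the earliest of:

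- (a) the day before the first subsequent oxygen-status record without advanced support, or, if there is no such oxygen-status record, the day before the first subsequent WHO score of 5 or less;
- (b) hospital discharge;
- (c) death.

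Use last visit or telephone contact only if none of these exists. Anchoring on the last record of advanced support keeps later re-escalations in the total. Taking oxygen status before the WHO score avoids mixing two sources that can disagree.

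Define off-support days as days before support starts, between episodes and after discharge. In Tables 14.2.3.2, 14.2.3.2.1 and 14.2.3.2.2, footnote the number of imputed dates by arm.

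The addendum gives the database lock as 26 April 2023, so the change should be labelled a post-lock correction of a derivation. It needs no new data. The cost is a few sentences, a small programming change and a rerun of three tables. Count the affected patients first: if there are none, a footnote saying so is enough.

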## **3.3 Secondary Efficacy Endpoints**

The secondary efficacy endpoints are:

- Clinical status by the 11-category WHO Clinical Progression Scale, at Day 8 (±1)
- Total duration of advanced oxygen support (high-flow nasal oxygen, extracorporeal membrane oxygenation [ECMO], non-invasive ventilation or mechanical ventilation).
- Percentage of patients in each study group requiring admission to intensive care unit (ICU) on Days 4, 8, 15 and 31.

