
The oxygen therapy rate on Day 8 between each dose of plitidepsin versus control arm will be compared using a stratified logistic regression model. The model will be adjusted for the randomisation stratification factors. The odds ratios, 95% CIs, and 2-sided p-values for the comparison of each dose of plitidepsin versus control arm will be presented.

Moreover, the percentage of patients who require oxygen therapy at some time from Day 1 to Day 4, from Day 1 to Day 8, from Day 1 to Day 15, and from Day 1 to Day 31, will be presented by treatment group. Clopper– Pearson 95% CI will be computed for the binomial proportions.

The difference in the percentage of patients who require oxygen therapy at some time during each period between each dose of plitidepsin versus control arm will be presented for each dose of plitidepsin and the exact 95% CI will be computed for the difference in the percentage.

The percentage of patients who require oxygen therapy at some time from Day 1 to Day 8 between each dose of plitidepsin versus control arm will be compared using a stratified logistic regression model. The model will be adjusted for the randomisation stratification factors. The odds ratios, 95% CIs, and 2-sided p-values for the comparison of each dose of plitidepsin versus control arm will be presented.

• *Time to intensification of respiratory support (WHO >6 [intubation]).* 

Time to intensification of respiratory support (in days), defined as the first day, from randomisation through completion of the study, on which a patient satisfies a category > 6 on the 11-point WHO Clinical Progression Scale.

Patients who reported a category > 6 on the 11-point WHO Clinical Progression Scale or died due to any cause through the study will be considered as an event on the first day on which a patient satisfies a category > 6 on the 11-point WHO Clinical Progression Scale or date of death, whichever occurs first. Otherwise, patients will be censored at the date of the last visit or telephone contact with the patient.

Time-to intensification of respiratory support (days) = (date of event or censoring – date of randomisation)

If date of event is the same as the randomisation date then time-to intensification of respiratory support will be considered as 1 day. If no data is available then time will be censored at time 0.

CONFIDENTIAL

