# Table 14.2.3.3 Patients who Require ICU Admission per Period (Full Analysis Set)

Period Variable	Plitidepsin 2.5mg (N=XXX)	Plitidepsin 1.5mg (N=XXX)	Control Arm (N=XXX)
From Day 1 to Day 4			
Require ICU Admission, n (%)	xx (xx.x)	xx (xx.x)	xx (xx.x)
95% CI for Require ICU Admission (%) [a]	XX.X – XX.X	$\mathbf{X}\mathbf{X}.\mathbf{X} - \mathbf{X}\mathbf{X}.\mathbf{X}$	$\mathbf{X}\mathbf{X}.\mathbf{X} - \mathbf{X}\mathbf{X}.\mathbf{X}$
Non Require ICU Admission, n (%)	xx (xx.x)	xx (xx.x)	xx (xx.x)
Difference of ICU Admission Rate (%) [b]	XX.X	XX.X	
95% CI for Difference of ICU Admission Rate (%) [c]	XX.X - XX.X	XX.X - XX.X	
From Day 1 to Day 8			
Require ICU Admission, n (%)	xx (xx.x)	xx (xx.x)	xx (xx.x)
95% CI for Require ICU Admission (%) [a]	XX.X - XX.X	XX.X - XX.X	XX.X - XX.X
Non Require ICU Admission, n (%)	xx (xx.x)	xx (xx.x)	xx (xx.x)
Difference of ICU Admission Rate (%) [b]	XX.X	XX.X	
95% CI for Difference of ICU Admission Rate (%) [c]	XX.X - XX.X	XX.X - XX.X	
Adjusted Odds Ratio [d,e]	X.XXX	X.XXX	
95% CI for Adjusted Odds Ratio [d,e]	x.xxx - x.xxx	x.xxx - x.xxx	
2-sided p-value [d]	X.XXX	X.XXX	
From Day 1 to Day 15			
Require ICU Admission, n (%)	xx (xx.x)	xx (xx.x)	xx (xx.x)
95% CI for Require ICU Admission (%) [a]	XX.X - XX.X	XX.X - XX.X	xx.x – xx.x
Non Require ICU Admission, n (%)	xx (xx.x)	xx (xx.x)	xx (xx.x)
Difference of ICU Admission Rate (%) [b]	XX.X	XX.X	
95% CI for Difference of ICU Admission Rate (%) [c]	XX.X - XX.X	XX.X - XX.X	

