# TFL Shells Labcorp Drug Development Study: 000000213894

From Day 1 to Day 31			
Require ICU Admission, n (%)	xx (xx.x)	xx (xx.x)	xx (xx.x)
95% CI for Require ICU Admission (%) [a]	XX.X - XX.X	XX.X - XX.X	XX.X - XX.X
Non Require ICU Admission, n (%)	xx (xx.x)	xx (xx.x)	xx (xx.x)
Difference of ICU Admission Rate (%) [b] 95% CI for Difference of ICU Admission Rate (%) [c]	XX.X XX.X – XX.X	XX.X XX.X – XX.X	

N = number of patients in analysis set; n = number of patients in each category; % = percentages are calculated based on N as the denominator; CI = Confidence interval; ICU = intensive care unit. [a] Clopper-Pearson 95% confidence interval.

[b] Difference of ICU Admission Rate = ICU Admission Rate for the plitidepsin arm - ICU Admission Rate for control arm.

[c] Exact 95% confidence interval.

[d] Adjusted Odds Ratio, 95% CI and 2-sided p-values based on a stratified logistic regression model with fixed effects of treatment group and randomisation stratification factors, ie, geographical region (Europe vs. Rest of the World), Charlson Comorbidity Index (0-1 vs. >1) and pre-baseline Barthel index ( $\geq$ 90 versus <90) as derived using the eCRF data as covariates. [e] Statistics calculated relative to Control Arm.

Reference: Listing 16.2.6.3

Programming notes (not part of the table):

• Table template TEF009A.

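### Deaths without ICU admission or invasive ventilation are counted as Non Require, so the Day 1 to Day 8 odds ratios can favour an arm with more early deaths

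*SAP*

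**What the plan says.** Section 3.3 lists among the secondary efficacy endpoints "Percentage of patients in each study group requiring admission to intensive care unit (ICU) on Days 4, 8, 15 and 31". Section 7.6.2.2 turns this into cumulative periods, beginning with "The percentage of patients who require admission to ICU at some time from Day 1 to Day 4". The formal comparison concerns "The percentage of patients who require admission to ICU at some time from Day 1 to Day 8 between each dose of plitidepsin versus control": the arms "will be compared using a stratified logistic regression model. The model will be adjusted for the randomisation stratification factors", with odds ratio, 95% CI and 2-sided p-value. The section has no rule for a patient who dies in the period without having been admitted.

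Shell Table 14.2.3.3 gives each period one row for patients who require ICU admission and one complementary row, "Non Require ICU Admission, n". Its footnote states "percentages are calculated based on N as the denominator; CI = Confidence interval; ICU = intensive care unit". There is no row for death.

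Invasive mechanical ventilation or ECMO is an other secondary endpoint (Section 3.5). Section 7.6.2.3 has it analysed like the oxygen therapy rate. Its per-period shell, Table 14.2.3.11.2, has the same two rows, the same denominator and the same Day 1 to Day 8 odds ratio and p-value.

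Death is handled differently in two other endpoints. In time to intensification of respiratory support (Section 7.6.2.3), a patient who reached a WHO category above 6 "or died due to any cause through the study will be considered as an event". For Day 8 clinical status (Section 7.6.2.2), a patient whose status is missing because of death is given category 10.

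**The concern.** Both tables ask whether escalation occurred, and death without escalation answers no. The comparison cannot separate a patient who never needed intensive care from one who died before reaching it. It appears among the efficacy analyses, and need for intensive care support is one of the three efficacy secondary objectives (Section 2.1.3.1). A reader will therefore take an odds ratio below 1 as benefit.

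Randomisation is stratified by Charlson index above 1 and Barthel index below 90 (Section 2.2), so frail patients can be enrolled, and death without ICU transfer is plausible in them. If one arm has more such deaths early on, its ICU and ventilation rates fall for the wrong reason. The description of intercurrent events in Section 6.2 does not mention death.

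**Working it through.** **Step 1: where a ward death goes.** Section 5.3 admits to the Full Analysis Set every randomised patient with at least one dose and one post-baseline clinical status. A later death does not remove the patient. The denominator is N, and the shell offers only Require and Non Require. A patient who dies on Day 5 without ICU admission can only be in Non Require. The SAP does not say this in words; it follows from the shell. The same reasoning applies to Table 14.2.3.11.2.

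**Step 2: algebra.** Let p be the proportion admitted to ICU in the period and d the proportion who die in the period without admission. The planned odds ratio uses p alone:

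OR(planned) = [p1/(1 − p1)] / [p0/(1 − p0)], with 1 = plitidepsin and 0 = control.

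The odds ratio for ICU admission or death uses p + d in place of p. Moving some percentage points from p1 to d1 lowers the planned odds ratio and leaves p1 + d1 unchanged.

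**Step 3: illustration.** The SAP states no rate, power or sample size for these endpoints, so there is no figure of its own to reproduce. The rates below are assumptions: ICU admission 8% to 20%, death without ICU 0% to 10%. In each row the proportion with ICU admission or death is equal in the two arms. The last two columns give the chance of a nominal 2-sided p < 0.05 favouring plitidepsin on the planned ICU rate, from an unadjusted two-proportion normal approximation. The first uses 203 per arm, the planned size (Section 2.3). The second uses 67 per arm, an assumption of about a third of that, because Section 8 says recruitment stopped before 33% of events.

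| ICU, control vs plitidepsin | Death without ICU, control vs plitidepsin | Planned OR | OR, ICU or death | 203 per arm | 67 per arm |
|---|---|---|---|---|---|
| 15% vs 15% | 3% vs 3% | 1.00 | 1.00 | 2.5% | 2.5% |
| 10% vs 9% | 1% vs 2% | 0.89 | 1.00 | 5.3% | 3.9% |
| 10% vs 8% | 2% vs 4% | 0.78 | 1.00 | 10.4% | 6.0% |
| 15% vs 13% | 3% vs 5% | 0.85 | 1.00 | 8.4% | 5.2% |
| 15% vs 12% | 3% vs 6% | 0.77 | 1.00 | 14.1% | 7.3% |
| 20% vs 15% | 5% vs 10% | 0.71 | 1.00 | 26.3% | 11.5% |
| 15% vs 10% | 3% vs 8% | 0.63 | 1.00 | 33.1% | 13.8% |

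For the row with ICU rates of 15% and 12%:
- Planned: (0.12/0.88)/(0.15/0.85) = 0.1364/0.1765 = 0.77.
- ICU or death: 0.12 + 0.06 = 0.18 and 0.15 + 0.03 = 0.18, so the odds ratio is 1.00.
- Chance at 203 per arm: SE = √[(0.15 × 0.85 + 0.12 × 0.88)/203] = 0.0339; 0.03/0.0339 = 0.885; Φ(0.885 − 1.960) = 0.141.

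The first row shows that equal rates in both arms do no harm. The problem needs a difference between arms in deaths without escalation.

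**The case against.** Patients ever admitted divided by all patients is a legitimate crude cumulative incidence with death as a competing event, and it describes ICU use correctly. The SAP never calls Non Require a success. A reader might infer that the plan scores a ward death as treatment success; the documents support only that such a death shares a cell with recovery.

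A reader might also infer that the SAP breaks its own rule on death. It has no general rule. Death belongs to the WHO-based endpoints because category 10 of that scale means dead, which is also a category above 6. ICU admission has no such category.

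Deaths are not hidden. Day 8 clinical status is compared with death as the worst category, mortality is reported at Days 4, 8, 15 and 31 with overall survival, and time to intensification includes death. These tests also lie outside the Hochberg procedure, which covers the primary and key secondary endpoints.

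All of this stands and limits the consequences. It does not answer the remaining point: a survival table leaves the ICU odds ratio and p-value as they are, and it does not show how many Non Require patients died without admission.

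**Conclusion.** The point holds for Tables 14.2.3.3 and 14.2.3.11.2. Their Day 1 to Day 8 comparisons, presented as efficacy, can favour an arm with more early deaths without escalation, and nothing in the tables would show it.

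The actual size is unknown, because the SAP gives neither ICU nor ward-death rates. Under the assumed rates, moving 1 to 5 percentage points from ICU admission to death without ICU gives planned odds ratios of 0.89 to 0.63 with no difference in ICU admission or death. The illustration shows direction and scale only; it is no evidence that such deaths occurred or differed between arms.

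The ICU rate is a secondary endpoint and the ventilation rate an other secondary endpoint. The primary and key secondary analyses are unaffected. A reader might conclude that a composite should replace the listed rate in every support table. The documents do not support that: the listed rate is a valid estimand, and the gap lies in reading it alone as efficacy.

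**What to change.** Keep the ICU-only and ventilation-only rates as listed, and make three additions:

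1. In Tables 14.2.3.3 and 14.2.3.11.2, add a row to each period for death in the period without ICU admission (or without invasive ventilation/ECMO).
2. Compare ICU admission (or invasive ventilation/ECMO) or death from any cause in the period, with the same stratified logistic model. Label it as an added analysis, since the SAP addendum (Section 1) dates database lock to 26 April 2023.
3. State that the ICU odds ratio is to be interpreted as an efficacy result only together with this composite.

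The cost is one derived flag from data already collected and a few table rows. The composite is less specific to ICU use, which the retained ICU-only rate covers. Extending it to high-flow oxygen and non-invasive ventilation is optional.
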